## 11.4 SAMPLING PROCEDURE, SAMPLE SIZE AND POWER CALCULATION

Sample size was determined based on the following power calculations:

For aim 1, a sample size of 28 subjects with 1:1 randomization were each measured at 4 time points provides 81.1% power to detect a 15 minute per day difference in PA between groups with a standard deviation of 19 minutes per day within each group and a within subject correlation of 0.7. A test based on a mixed-model analysis is anticipated at a significance level of 0.05.

For aim 2, a sample size of 50 subjects with 1:1 randomization provides 80.2% power to detect an 8% difference in KCCQ score between groups with a standard deviation of 10 in KCCQ score within each group and an alpha of 0.05.

## 11.5 COMPUTATION OF DERIVED VARIABLES

Weekly averages:

1. Baseline mean: Average of all measurements in a month prior to randomization.
2. Week 4 mean: Average of all measurements in week 4.
3. Week 8 mean: Average of all measurements in week 8.
4. Week 12 mean: Average of all measurements in week 12.
5. Change from baseline to Week 12 mean: Difference of week 12 mean from baseline mean.
- 1.

## 11.6 ACCEPTANCE CRITERIA

Subjects will be screened and selected based on methods described in Section 5. All subjects who were enrolled will be classified based on the analysis populations described in Section 11.1. Missing data will be dealt with as described in Section 11.12.

## 11.7 TABLES, GRAPHS, STATISTICAL MODELS AND TESTS FOR ANALYSIS

Please refer to the Statistical Analysis Plan for tables, graphs, models and tests.

## 11.8 ENDPOINT ANALYSIS

### 11.8.1 PRIMARY ENDPOINT ANALYSIS

General statistical approach to primary endpoint: This endpoint will be analyzed in both the ITT and PP populations. Missing data will be handled as described in Section 11.12.

Analysis strategy for P1:

The outcome variable for this objective is the median Abbott ICD and CRT-D device measured daily PA obtained over the 1 week before randomization (baseline) and week 4, week 8, and week 12 after randomization. This endpoint represents a summary measure. The hypothesis test will evaluate whether the trajectory of the mean Abbott ICD and CRT-D device measured in the remote CR treatment group is different from the trajectory in the usual management group. The test will be a multilevel modeling (aka mixed models) on trajectories of the outcomes over the study period.

P1: Compare the trajectory of the median Abbott ICD and CRT-D device measured daily PA obtained over the 1 week before randomization (baseline) and week 4, week 8, and week 12 after randomization among patients randomized to remote CR versus usual management.

Reporting for P1: Descriptive summaries of the median physical activity at baseline and 4 weeks, 8 weeks, and 12 weeks after randomization will be presented by treatment group. The estimated differences in slopes of trajectories from CR and usual care treatment groups will be presented, along with the p-values by comparing the trajectories over study period. If differences are noted with regard to baseline covariates adjusted analyses will be performed for the primary endpoint.

### 11.8.2 SECONDARY ENDPOINT ANALYSIS

General statistical approach to secondary endpoints: These endpoints will be analyzed in both the ITT and PP populations. We will not be using methods to account for multiplicity (alpha sharing plan) as this is a hypothesis generating rather than a confirmatory study. Missing data will be handled as described in Section 11.12.

Analysis Strategy for S1: Will be similar to what is described for P1 with different endpoints.

S1: Compare the change in mean HF symptom severity scores at baseline and 12 week as measured by Kansas City Cardiomyopathy Questionnaire (KCCQ) among patients randomized to remote CR versus usual management.

Reporting for S1: Will be similar to what is described for P1 with different endpoints. If differences are noted with regard to baseline covariates adjusted analyses will be performed for the secondary endpoints.

**S2: (Safety) Report Adverse Events of the combination of heart failure hospitalization, fracture, myocardial infarction, serious adverse arrhythmia, and ICD therapy.**

Reporting for S2: A listing of Adverse Events will be produced for the study population.

**Analysis Strategy for S3:** This analysis strategy will be implemented for the S4 analyses. The outcome variable for this objective is the HF symptoms severity score as measured at baseline through end of follow up. This endpoint represents repeated measures. The hypothesis test will evaluate whether there is a correlation between these treatment groups. If data are normally distributed, the test will be a Pearson correlation test. Otherwise, we will use a Spearman correlation test.

**S3: Investigate the correlation between change in daily PA as measured by the Abbott ICD or CRT-D device between baseline and end of follow up and change in HF symptoms severity scores as measured by KCCQ during same time period.**

Reporting for S3: We will be reporting the strength of the correlation and related p values.

#### **11.8.3 MULTIPLICITY**

Since this is an exploratory/pilot/hypothesis generating study, we will not adjust alpha level for multiple tests. All tests will have an alpha level of < 0.05.

#### **11.9 LEARNING CURVE EFFECTS**

NA

#### **11.10 INTERIM ANALYSIS PLAN**

NA

#### **11.11 SENSITIVITY ANALYSIS**

The sensitivity Analysis will be considered for P1 ITT analysis:

Multilevel modeling after imputing missing data using MI: This sensitivity analysis will be performed with the same method as the main analysis, but with imputation for missing data as described above.

Multilevel modeling assumption not met: This sensitivity analysis will be performed if the Multilevel modeling assumptions severely violated and data transformation needed. If that is the case, we will run multilevel model on the transformed data and the p-value will be compared to the main results. The estimated differences in slopes of trajectories and respective p-values will be presented.

#### **11.12 MULTILEVEL MODELING OF ENDPOINTS P1 AFTER ADJUSTING FOR BASELINE**

DATA: THIS SENSITIVITY ANALYSIS WILL BE PERFORMED SAME AS ORIGINAL ANALYSIS ADJUSTING FOR THE BASELINE MEAN IN THE MODEL AS A COVARIATE. THE SIGNIFICANCE OF THE TREATMENT ASSIGNMENT VARIABLE WILL BE TESTED. THE ESTIMATED ADJUSTED DIFFERENCES IN SLOPES OF TRAJECTORIES AND RESPECTIVE P-VALUES WILL BE PRESENTED AND COMPARED TO THE MAIN RESULTS. CONFOUNDING VARIABLES, MISSING DATA AND BIAS

Confounding: patients entering weight loss programs which promote exercise, surgeries which reduce body fat by significant degree, getting a physical trainer during course of study.

Missing Data: When using weekly averages (P1), will take the median of the existing values for that week and use that value to impute the missing values for patients.

Weekly missing values will be handled using Multiple Imputation (MI) approach. Bias: The study sample size is reasonably small introducing the possibility of selection bias. To minimize this risk, we are employing simple, straightforward inclusion and exclusion criteria and minimizing the total number of criteria to make our study population as similar to a general HF population as possible. Other sources of bias, including misclassification bias will be minimized by the direct electronic dataflow from randomization to data capture from the Pattern Health App, and direct data streams from Abbott medical to the Pattern Health app. Recall bias will be minimized because questions regarding symptoms will be asked to reflect the current symptoms, not a recollection of prior symptoms. Observer bias will be minimized by the objective nature of the physical activity measurement used in the primary endpoint.

## 12 STUDY ADMINISTRATION

### 12.1 STUDY CONDUCT, REGULATORY AND ETHICAL CONSIDERATIONS

#### 12.1.1 ETHICAL CONDUCT OF THE STUDY

The investigator will conduct the study in accordance with GCP and all applicable regulations, including, where applicable, the Declaration of Helsinki. The study will also be carried out in keeping with applicable national and local laws and regulations. This may include an inspection by the sponsor's representatives and/or regulatory authority's representatives at any time.

#### 12.1.2 ETHICS APPROVAL

The investigational site's IRB must meet all relevant regulatory requirements. The study protocol and ICF will be reviewed by the IRB prior to enrolling participants into the study. The investigator is responsible for submitting all protocol or ICF changes and SAE reports to the IRB according to local procedures.

In accordance with applicable local regulatory requirements, the investigator may be obligated to provide periodic safety updates on the conduct of the study at his or her research site and notification of study closure to the IRB. Such periodic safety updates and notifications are the responsibility of the investigator.

### 12.2 STUDY REGISTRATION

The study team will register the study with ClinicalTrials.gov prior to enrollment of any subjects.

### 12.3 INVESTIGATOR RESPONSIBILITIES

#### 12.3.1 REPORTING REQUIREMENTS

By participating in the study, the principal investigator agrees to submit reports of any serious adverse events (SAEs) incidences according to the specific timeline as outlined in Section 14.3.6. The investigator will also agree to submit reports to the IRB as appropriate. As required by NESTcc, the investigator will provide accurate reporting to both the sponsor organization and NESTcc for preliminary scientific results, final scientific results, progress reporting and all other reporting requirements as outlined in the Scope of Work.

#### 12.3.2 SOURCE DOCUMENTATION

The Investigator of the study will agree to maintain satisfactory case histories for study participants that have received treatment or been involved in a study intervention. Also, the investigator agrees to maintain accurate source documentation as part of the case histories.

#### 12.3.3 RECORD RETENTION

The investigator shall maintain the records required for this investigation for a period of 5 years after the date on which the investigation is terminated or completed. The research data collected in this study will be kept indefinitely.

#### 12.3.4 FINANCIAL DISCLOSURE AND OBLIGATIONS

The investigator of this study is required to provide financial disclosure information to allow the sponsor of the study to submit the complete and accurate certification or disclosure documents under 45 CFR 45, if applicable.

## 12.5 SAFETY OVERSIGHT

Due to the short time between trial startup and completion along with the single center study design and relatively small number of enrolled subjects no DSMB will be convened for the project.

The likelihood of serious adverse events occurring as a result of participation in this study is minimal. Project Aim 4 is designed to assess the safety of remotely administered CR. Data sources to ascertain the combination safety endpoint will include answers to questionnaires administered through the patient smartphone application, review of the Duke EMR and review of electrogram data from the implantable device.

## 12.6 CLINICAL MONITORING

Monitoring of the study site will be performed by the sponsor's designated monitor(s). No on-site visits are scheduled. Eligibility, ICF and safety outcomes will be monitored remotely.

By signing the protocol, the investigator agrees that, within local regulatory restrictions and institutional and ethical considerations, authorized representatives of the sponsor, a regulatory authority, and/or an IRB may visit the site to perform audits or inspections, participant charts and source documents, and other records related to study conduct. The purpose of the sponsor audit or inspection is to systematically and independently examine all study-related activities and documents to determine whether the study-related activities were conducted, and data recorded, analyzed, and accurately reported according to the protocol, the site's standard operating procedures, GCP guidelines of the ICH, and any applicable regulatory requirements. The investigator should contact the sponsor immediately if contacted by a regulatory agency regarding an inspection.

## 12.7 TERMINATION OF STUDY

The sponsor reserves the right to temporarily suspend or prematurely discontinue this study at any time and for any reason. If such action is taken, the sponsor will discuss this with the investigator (including the reasons for taking such action) at that time. The sponsor will promptly inform any other investigators and/or institutions conducting the study, if the study is suspended or terminated for safety reasons and will inform the regulatory authorities of the suspension or termination of the study and the reason(s) for the action. If required by applicable regulations, the investigator will inform the IRB promptly and provide the study participants with the reason for the suspension or termination. If the study is prematurely discontinued, all study data will be returned to the sponsor.

## 13 INSTITUTIONAL REVIEW BOARD (IRB)

The Duke IRB will function as the IRB of record for this protocol.

Institutional Review Board (IRB) approval for the CIP and the ICF will be obtained by the PI prior to screening, consenting and enrolling patients in the clinical investigation. The approval letter must be received by the Sponsor. The IRB will be responsible for assuring the CIP and ICF comply with applicable regulatory requirements (e.g., 45 CFR Part 46, 21 CFR Part 50, 21 CFR Part 56) and ICH GCP.

Any amendments to the CIP as well as associated ICF changes will be submitted to the IRB and written approval obtained prior to implementation, according to IRB requirements.

No changes will be made to the CIP or ICF or other written information provided to the patient without appropriate approvals, including the IRB and the Sponsor.

Until the clinical investigation is completed, the PI will advise his IRB of the progress of the clinical investigation, per IRB requirements. Written approval must be obtained from the IRB yearly to continue the clinical investigation, according to the IRB requirements.

No investigative procedures other than those defined in the CIP will be undertaken on the enrolled subjects without the agreement of the IRB and the Sponsor.

## 14 MANAGEMENT OF PROTOCOL AMENDMENTS, DEVIATIONS AND ADVERSE EVENTS

### 14.1 PROTOCOL DEVIATIONS, AMENDMENTS AND VIOLATIONS

A study deviation is defined as an event within the study that did not occur according to the Clinical Investigative Plan (CIP). Investigators are not allowed to deviate unless it is necessary to protect the safety, rights, or well-being of a subject in an emergency or in unforeseen situations beyond the investigator's control. Any significant protocol deviation will be reported to the IRB as soon as possible. If the investigator anticipates, contemplates, or makes a conscious decision to deviate, in other situations, the study sponsor should be notified and asked for approval in advance.

All study deviations must be reported to NESTcc and the Sponsor with an explanation for why the deviation occurred. In the event a deviation occurred to protect the life or physical well-being of a subject in an emergency, the deviation must be reported to the IRB and to the sponsor within five (5) working days. Reporting of all other deviations should comply with the IRB policies and be reported to the sponsor as soon as possible. The sponsor and PI will review all reported deviations on a periodic basis, assess their significance, and identify any corrective or preventive actions (eg. amend the CIP, conduct additional site training, or terminate the investigation).

We do not anticipate any protocol deviations, however during the course of the study patients may accidentally be provided inaccurate information through the Pattern Health app that breaks the randomization or is not in compliance with the exercise prescription as provided by the trained physiologist. To avoid this, the app functionality has safeguards in place limiting the flow of data to the patient's smartphone to only the components approved in the study protocol.

Treatment non-compliance with the prescribed exercise regimen has the potential to reduce the observed effect size from randomization. To reduce the effect of non-compliance and patient withdrawal, we will carefully assess the patient's willingness to exercise and periodically engage with the smart phone application during the baseline phase prior to enrollment. Patients who are reluctant to participate in the full 12 week trial will be excluded.

### 14.2 ADVERSE EVENTS (AES) AND SERIOUS ADVERSE EVENTS (SAES)

#### 14.2.1 DEFINITION OF AN ADVERSE EVENT

An adverse event is defined as any untoward medical occurrence associated with the use of an intervention in humans, whether or not considered intervention-related (21 CFR 312.32 (a)).

#### 14.2.2 DEFINITION OF A SERIOUS ADVERSE EVENT

An adverse event (or a suspected adverse reaction) is considered "serious" if it has been determined by either the investigator or sponsor that a particular event results in the following outcomes: a life-threatening adverse event, significant or persistent state of incapacitation (or severe disruption of normal daily functions), a congenital anomaly/birth defect, inpatient hospitalization (or lengthened hospitalization) or death. In the event important medical events that do not result in death (but require hospitalization or is life threatening) can be classified as a serious adverse event with appropriate medical judgement when interventions related to the study jeopardize the study participant (and

require medical or surgical intervention to prevent any of the outcomes listed in the definition of a serious adverse event).

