### 9.2.3 ADVERSE EVENTS OF SPECIAL INTEREST

AEs of special interest (AESIs) defined for this trial include: heart failure hospitalization, fracture, myocardial infarction, serious adverse arrhythmia, and ICD therapy. Certain disease-related events (DREs) that are common within the study population will not be reported. This includes chest pain, hyper or hypotension, hyper or hypoglycemia, muscle or joint pain, shortness of breath or breathlessness, fatigue, diaphoresis, or depression.

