#### 14.2.4 ADVERSE EVENT REPORTING

Timely, accurate, and complete reporting and analysis of safety information for clinical studies are crucial for the protection of subjects. Reporting and analysis of safety data are mandated by regulatory authorities worldwide. AE CRF's will be collected for all AEs that are potentially study-related and all serious AEs regardless of their relationship to the study. For AEs that require immediate reporting, initial reporting may be done by phone, fax, email or on the CRF completing as much information as possible. The AE CRF must be completed as soon as possible. For any changes in status of a previously reported adverse event (i.e. change in actions taken, change in outcome, change in relatedness), an update to the original AE must be completed. All reported AEs must be followed until the AE has been resolved, is unresolved with no further actions planned, the subject dies or exits the study, or until study closure, whichever occurs first. In the event that a subject is exited from the study prior to study closure, all efforts should be made to continue following the subject until all unresolved system related AEs, as classified by the investigator, are resolved or they are unresolved with no further actions planned. At the time of study exit, all collected AEs with an outcome of "Unresolved, further actions or treatment planned" must be reviewed and an update to the original AE must be reported. At a minimum, if there are no changes to the description, relatedness, test and procedures or actions taken, the outcome must be updated to reflect "Unresolved at time of study closure."

All AEs will be reported to the sponsor and the IRB within 10 working days of the event.

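### The important-medical-event sentence in the SAE definition covers only events that are already serious, so events treated in time to prevent a serious outcome get the 10-working-day clock instead of immediate reporting

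*Protocol*

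**What the plan says.** **Definition (Protocol 14.2.2).** The first sentence lists outcomes that make an event serious once the investigator or the sponsor has so determined. Among them are "a life-threatening adverse event", a "significant or persistent state of incapacitation (or severe disruption of normal daily functions", and "inpatient hospitalization (or lengthened hospitalization) or death". It sets no condition on cause, relatedness or arm.

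The second sentence deals with important medical events. It says that "important medical events that do not result in death (but require hospitalization or is life threatening) can be classified as a serious adverse event", and continues "with appropriate medical judgement when interventions related to the study jeopardize the study participant". A closing parenthesis adds that medical or surgical treatment must be needed to avert one of the outcomes already listed.

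**Consequences of the class (Protocol 14.2.4, 14.2.5 and Table 4).** AE forms "will be collected for all AEs that are potentially study-related and all serious AEs regardless of their relationship to the study". For adverse events in general, 14.2.4 states: "All AEs will be reported to the sponsor and the IRB within 10 working days of the event". For serious events, 14.2.5 and Table 4 require the investigator to tell the sponsor and NESTcc at once, with the IRB informed under local rules.

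**Events of special interest (Protocol 9.2.3).** These are "heart failure hospitalization, fracture, myocardial infarction, serious adverse arrhythmia, and ICD therapy". The list is separate from the SAE definition, and no reporting time is attached to it.

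**The concern.** An important-medical-event clause exists to catch events that have not reached a listed outcome, usually because someone intervened in time. The closing words of this one show that purpose. Its opening parenthesis, however, admits only events that need hospitalisation or threaten life, and the first sentence has already made those serious. The clause is circular.

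It also ties these events to study interventions. The first sentence has no such link, and 14.2.4 treats serious events alike whatever their relation to the study.

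What is at stake is reporting speed for a narrow group of events. The trial has no DSMB (10.3, 12.5). The exercise programme runs without in-person instruction or cardiopulmonary exercise testing (1.4), and the protocol itself says little is known about the safety of starting that way (9.1, Aim 3). The sponsor's early view of safety therefore depends largely on which events are classed as serious.

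**Working it through.** The point turns on wording, and the plan has no figure to reproduce. The check reads each sentence of 14.2.2 as a set of conditions and runs four kinds of non-fatal event through it.

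**Conditions**

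- Sentence 1: life-threatening, *or* incapacitating or severely disrupting daily function, *or* inpatient or lengthened hospitalisation (death and congenital anomaly are set aside here). Any one suffices.
- Sentence 2: (needs hospitalisation *or* is life-threatening) *and* study interventions put the participant in jeopardy *and* treatment is needed to avert a listed outcome. Even then the classification is optional.

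**Result**

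| Non-fatal event | Sentence 1 | Sentence 2 | Report to sponsor |
|---|---|---|---|
| Inpatient admission, either arm | Serious | Within its scope, but adds nothing | Immediately |
| Not admitted, life-threatening | Serious | Within its scope, but adds nothing | Immediately |
| Not admitted, not life-threatening, but incapacitating or severely disruptive | Serious | Not reached | Immediately |
| None of these, but needs treatment to prevent one of them | Not serious | Not reached | Within 10 working days |

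The last row is the gap. An ICD therapy, arrhythmia or fracture can fall there, so three of the five special-interest events are open to it. That such events can occur without admission is a clinical assumption, not a statement in the documents.

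**Does anything else close the gap?**

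- *Severity grade.* 14.2.3 says that severe and serious need not coincide, and gives severe events no clock.
- *Special-interest status.* 9.2.3 attaches no clock.
- *Immediate reporting of other events.* 14.2.4 and 14.2.5 mention adverse events that need immediate reporting without saying which they are. The only stated immediate requirement is for SAEs.
- *NESTcc.* Table 4 sends SAEs to NESTcc immediately. The 10-day rule in 14.2.4 names only the sponsor and the IRB.

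**Length of the delay.** Assuming five working days a week and no holidays, 10 / 5 = 2 calendar weeks. The intervention period is 12 weeks, so the permitted delay is up to 2 / 12 = 1/6 of it, about 17%.

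**Internal contradiction.** A treatment that averts a listed outcome implies that the outcome has not yet occurred. An event that is already life-threatening has met a listed outcome, and one that leads to admission meets another. Read together, the two parentheses leave the clause almost no event of its own.

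**The case against.** The strongest reply is that sentence 1 is the operative test and is broad. It covers a life-threatening arrhythmia with no admission and a disabling fracture treated at home, and either the investigator or the sponsor can make the determination. That stands. A reader might infer from sentence 2 that ICD therapy, arrhythmia or fracture can never be serious without admission. The documents do not support this: the life-threatening limb appears in both sentences, and the incapacitation limb in sentence 1 applies as well. Only the last row of the table is left out.

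A reader might also infer that the same hospitalisation could be graded differently by arm, because the trial is open label and usual care does not receive the exercise prescription. The documents do not support that either. Sentence 1 makes every inpatient hospitalisation serious in both arms, nothing in sentence 2 takes that away, and 14.2.4 collects serious events whatever their relation to the study. What remains is an ambiguity: sentence 2 describes hospitalised events as optionally serious with a link to study interventions, beside a sentence that makes them serious outright.

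Nor does the safety endpoint lose events. The S2 listing is built on the special-interest events with no filter on seriousness (Protocol 11.8.2; SAP 6.4 and 7). Protocol 10.1.1 says that all adverse events go into the eCRF, 10.1 adds a record screen at study end, and 12.5 adds review of device electrograms. Serious adverse arrhythmia is not defined, but nothing ties that term to 14.2.2. Section 10.1.1 also sits in tension with the narrower AE-form rule in 14.2.4, so loss of data on unrelated non-serious events cannot be asserted.

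Finally, the definition does not decide what other participants are told. Section 14.2.6 covers related events whether serious or not, and the discontinuation criterion in 6.4 refers to adverse events in general.

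It could be said that sentence 2 has a sliver of its own: an event that needed hospitalisation but led to no inpatient stay. Even so, it does not reach events that needed no hospitalisation, which are the ones at issue.

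**Conclusion.** The point holds in a narrow form. The important-medical-event sentence repeats categories that sentence 1 already makes serious, adds a link to study interventions that neither sentence 1 nor 14.2.4 has, and contradicts its own closing words. An event that is not admitted, not life-threatening and not incapacitating, but needs treatment to prevent such an outcome, cannot be classed as serious. It is reported to the sponsor within 10 working days instead of immediately.

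The number of events affected cannot be stated, because the documents give no event rates. The conclusion rests on reading the parenthesis in sentence 2 as limiting the clause, which is its plain sense, and on the clinical assumption that such events occur. The effect is on reporting class and speed. It does not touch the primary endpoint, the S2 listing or the seriousness of any hospitalisation in either arm. The wording is still worth correcting, because the rule as written gives the wrong reporting class in a trial with no DSMB.

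**What to change.** Replace the second sentence of Protocol 14.2.2 with text to this effect:

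> An important medical event that is not fatal, is not life-threatening and does not lead to hospitalization is also serious if, by medical judgement, it jeopardizes the participant or needs medical or surgical treatment to prevent one of the outcomes above. This applies in both arms, whatever the relation of the event to the study intervention.

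This removes the circular parenthesis, restores the preventive purpose, and brings the sentence into line with sentence 1 and with 14.2.4. Correcting the parenthesis alone would not be enough: the link to study interventions would remain, and the clause would then operate mainly in the arm that receives the exercise prescription.

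The cost is one sentence in a protocol amendment and a few more SAE reports in a trial planned for 50 patients. No analysis changes.
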